6.1.8.3 Treatment compliance

Treatment compliance of study drug is calculated on the basis of both eCRF (i.e. data collected from drug accountability and study drug exposure pages) and eDiary-entry respectively.

Treatment compliance based on the eCRF by TP is defined as

$$\left(\frac{\text{Extent of exposure in TPx (eCRF)}}{\text{Treatment duration in TPx excluding break(eCRF)}} \right) \times 100\%, \text{ where } x=1, \dots, n.$$

Overall treatment compliance based on eCRF is calculated as

$$\left(\frac{\text{Overall extent of exposure(eCRF)}}{\text{Overall treatment duration excluding breaks(eCRF)}} \right) \times 100\%.$$

Treatment compliance based on eDiary-entry by TP is defined as

$$\left(\frac{\text{Extent of exposure in TPx (eDiary)}}{\text{Treatment duration in TPx excluding break(eCRF)}} \right) \times 100\%, \text{ where } x=1, \dots, n.$$

Overall treatment compliance based on eDiary is calculated as

$$\left(\frac{\text{Overall extent of exposure(eDiary)}}{\text{Overall treatment duration excluding breaks(eCRF)}} \right) \times 100\%.$$

For treatment group A2, treatment compliance by TP will be calculated based on a 168-day period.

Data on duration of treatment, compliance, and used tablets will be presented by listings.

Extent of exposure and treatment compliance for treatment group B will not be analyzed.

6.2 Efficacy

6.2.1 Primary efficacy variable

Not applicable.

6.2.2 Secondary efficacy variable

The analyses for all the secondary efficacy variables will be conducted in the FAS population.

The secondary efficacy variable is number of bleeding days, as defined in Section 4.5.

Number of bleeding days will be shown by treatment groups for the treatment phase only plus 1 or 2 bleeding periods following the end of the last TP depending on treatment regimen.

6.2.3 Other efficacy variables

The analyses for all other efficacy variables will be conducted in the FAS population.

6.2.3.1 Volume of menstrual blood loss related variables

- Volume of menstrual blood loss per 28 days (assessed by MP)
- Volume of menstrual blood loss per bleeding episode (assessed by MP) for first, second, and third bleeding episode after the end of treatment
- Volume of MBL per bleeding episode within the treatment break. All days of the bleeding episodes will be used even if some days of the episode lie outside the treatment break. The first, second and third bleeding episode will be considered. This endpoint is only applicable for VPR groups.
- Amenorrhea (yes/no), defined as menstrual blood loss <2 mL during last 28 days of treatment, based on the MP

- Absence of bleeding (spotting allowed) during the last 28 days of the treatment; based on the UF-DBD

Analysis for volume of menstrual blood loss per 28 days will be done by treatment group and Time interval D (according to [Figure 4-1](#)). Amenorrhea and absence of bleeding will be analyzed by treatment group and TP. For treatment group B, volume of menstrual blood loss per bleeding episode (assessed by MP) for first, second, and third bleeding episode after the end of treatment will only be done after the reference end date. Volume of MBL per bleeding episode within the treatment break for treatment group B will not be analyzed.

6.2.3.2 Time to event related variables

- Time to onset of amenorrhea for each treatment period
- Time to onset of controlled bleeding for each treatment period
- Time to start of bleeding after last study drug intake (assessed by the UF-DBD).

Time to event related variables and censoring rules are defined in [Section 4.5](#).

Time to onset variables will be analyzed using the Kaplan-Meier estimates (including number of events, number of censored, 25th, median, and 75th percentiles). This analysis will be performed using the calendar time (days) as unit. Kaplan-Meier plots will also be presented. The analysis will be done by treatment group and TP (time intervals B according to [Figure 2](#), excluding screening and FUP). For treatment group A2, TP per 168-day defined in the protocol will be used and shown separately.

Time to start of bleeding after last study drug intake for treatment group B will not be analyzed.

6.2.3.3 Ultrasound examination related variables

- Percent change in volume of largest fibroid compared to baseline (baseline = last value obtained before randomization; measured by ultrasound examination)
- Percent change in volume of 3 largest fibroids compared to baseline (measured by ultrasound)
- Percent change in volume of uterus compared to baseline (measured by ultrasound)
- Percentage of subjects with a volume reduction of $\geq 25\%$ of the 3 largest fibroids (measured by ultrasound)
- Percentage of subjects with a volume reduction of $\geq 25\%$ of the largest fibroids (measured by ultrasound)
- Percentage of subjects with a reduction of $\geq 25\%$ of uterine volume (measured by ultrasound)

Analysis will be done by treatment group and visit/time interval B (according to [Figure 4-1](#)).

If multiple volume assessments by ultrasound are available for a time period, the smallest volume will be used for the baseline time period, and the largest volume will be used for any other time periods of Intervals B.

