4.5 Data Rules

Reference Start/End dates

For vilaprisan (VPR), the reference start and end dates refer to the first and last study drug intake and will be identified based on the eCRF entry (EXCATN=1). For subjects with study drug exposure unknown, the randomization date will be used as the reference start date, and the end date of last scheduled/ unscheduled visit according SV (Subject Visits dataset) will be used as the reference end date.

Missing or partially missing eCRF end dates will be replaced by the date of the last study drug intake according to the diary. In case there is no study drug intake recorded in the diary, the date of the last available visit/contact will be used, which is the maximum of the end date of last scheduled/ unscheduled visit according SV (Subject Visits dataset), and the “last visit” as collected on the eCRF page for Disposition dataset. For subjects randomized to VPR who did not take any treatment (FAS not SAF), the last available visit date will be used as the reference start date and the reference end date.

For treatment group B the reference start date is defined by the randomization date. The reference end date is defined by the start date of the End of Treatment (EoT) visit (unscheduled EoT visits not considered). Missing EoT visit dates will be replaced by the end date of the last available visit before the safety closeout visit (refer to Table 4-1). If a subject in treatment group B has no safety

closeout visit, missing EoT visit dates will be replaced by the date of last scheduled/ unscheduled visit according SV (Subject Visits dataset).

For both VPR and treatment group B, the reference end date after the missing replacement with the rules defined above should be no earlier than the reference start date. Otherwise, the reference end date will finally be replaced by the reference start date.

For any analysis, if date of first study drug exposure/ date of last study drug exposure is used, the reference start/end date for treatment group B defined as above will be used for the analysis in treatment group B, if applicable.

Table 4-1 Replacement rules for missing reference start/end dates and TP start/end dates

	Choice	VPR regimens	Treatment group B
Reference start date	1 st	eCRF	Randomization date
	2 nd	a. If study drug exposure unknown, use randomization date b. If no study drug exposure (FAS not SAF) use SV last visit end date	
Reference end date / Last TP end date	1 st	eCRF	EoT visit start date

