Exit examination	BL, last value within interval																		Exit examination (Start: EoT -7 days); last value within this interval								

Abbreviations: BL: Baseline, TP: Treatment Period, BR: Break (not applicable for Treatment group B), FUP: Follow-up, d: days, m: months.

Treatment periods and breaks will be identified as described above. Baseline/Pre-treatment phase starts with the date of informed consent and ends on the day before the start of the Treatment phase.

The Treatment phase starts and ends with the reference start and end date. The FUP phase starts on the day after the end of the treatment phase and ends on the maximum of the last date at which a visit took place (visit end date), and the “last visit” as collected on the eCRF page. For patients who did not complete the planned schedule of TPs, a break period will be defined after the end of the last TP, as described in the previous subsection ‘Break period’. This break period will be followed by the FUP.

Baseline, Treatment phase, FUP phase, TPs and breaks are subdivided into subsequent periods of different lengths (28, 84, or 168 days). Exit examination time intervals include the baseline measurement, i.e. the last non-missing value before reference start date, and the exit examination which is defined as the last non-missing value at or after the reference end date – 7 days, which is per definition the safety closeout visit for subjects who perform this visit.

For treatment group B, consecutive TPs (84-day time intervals) in the treatment phase will be used for intervals B and intervals C. Each TP will be subdivided into subsequent consecutive 28-day periods for intervals D. For intervals for assessing AEs in the treatment phase, consecutive TPs will be ended at day 60 after the reference end date. For the assessment in the follow-up phase, same rules will be used as VPR treatment groups.

Details on time intervals for AE presentation are given in Section 6.5.3.5.

Details on time intervals for BMD presentation are given in Section 6.5.1.

Break period

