In general, the last valid, non-missing value prior to the Reference start date will be considered as baseline value. For variables analyzed by 28-day periods, the baseline period corresponds to the last 28 days before the reference start date. This definition does not apply to analyses related to menstrual blood loss where a specific definition for baseline menstrual blood is defined (see baseline menstrual blood loss for 28 days).

Bleeding caused by conducting endometrial biopsy

If an endometrial biopsy was conducted, bleeding on the day of intervention and the 3 days thereafter will not be considered in the bleeding related evaluation, i.e., bleeding/spotting on the day of biopsy and 3 days thereafter will not be considered as day(s) with bleeding/spotting and MP values will be set to 0 mL. This rule is applicable for all bleeding related efficacy analyses.

A biopsy will be regarded as conducted if the intervention was attempted, either successfully or unsuccessfully. Successful means that the date of biopsy is given and 'Biopsy sample obtained - Not done' is not ticked in the eCRF. Unsuccessful means that the date of biopsy is given, 'Biopsy sample obtained - Not done' is ticked in the eCRF, and the reason 'Unsuccessful attempt' is selected.

Baseline menstrual blood loss for 28 days

Baseline menstrual blood loss for 28 days is defined as the sum of volume of menstrual blood loss data of respective days in the baseline cycle. If baseline cycle length is more than 28 days, only data from the first day of cycle to the 28th day of cycle will be used. If baseline cycle length is less or equal than 28 days, data from the first day of cycle to the last day of cycle will be used.

Baseline menstrual cycle

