6.1.2 Demographic, Baseline Characteristics

Demographics and baseline characteristics will be recorded during screening period. As specified in Section 4.5, the measurement closest to the administration of study drug will be used as baseline. All demographic and baseline characteristics will be listed and summarized by treatment and in total according to current existing BHC Global Standard Tables. The descriptive statistics will be presented for the SAF, modified SAF, and FAS.

Demographic and baseline assessments to be summarized will include:

- Age, region/ country and race, ethnicity
- Weight, height, body mass index (BMI)
- Categorized BMI group (<18.5, 18.5-<25, 25-<30, ≥30 kg/m²)
- Smoking and alcohol consumption
- Baseline BMD of lumbar spine, hip and femoral neck
- Baseline BMD of lumbar spine, hip and femoral neck by scan type (Lunar, Holgic and other)
- Baseline endometrial thickness
- Uterine fibroids visualized at baseline (Yes/No)
- The largest diameter of the largest fibroid, volume of largest fibroid, volume of 3 largest fibroids, location of largest fibroid (measured by ultrasound) at baseline. Baseline uterine volume, endometrial thickness (measured by ultrasound)
- Baseline MBL (by MP) and categorized MBL group (≤80 mL, 80< -150 mL, 150 <- 300 mL, 300 < - 500mL and >500 mL)
- Baseline hemoglobin
- Education (years of education, university/colleague degree)

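### SAP Section 6.2.3.3 gives two baseline rules for largest-fibroid volume, last before randomization and smallest in the baseline period, and does not say which prevails

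*SAP*

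**What the plan says.** Section 6.2.3.3 lists six ultrasound variables: percent change from baseline in the volume of the largest fibroid, of the three largest fibroids and of the uterus, and the percentage of subjects with a reduction of at least 25% in each.

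- The first bullet, for the largest fibroid, carries its own definition: "baseline = last value obtained before randomization; measured by ultrasound examination".
- The closing sentence, on repeat assessments, reads in part: "the smallest volume will be used for the baseline time period, and the largest volume will be used for any other time periods". The post-baseline half refers to Intervals B.

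Other parts of the SAP bear on the same choice:

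- Section 4.5, time intervals: "Baseline/Pre-treatment phase starts with the date of informed consent and ends on the day before the start of the Treatment phase".
- Section 4.5, reference dates: for vilaprisan "the reference start and end dates refer to the first and last study drug intake"; "For treatment group B the reference start date is defined by the randomization date".
- Section 4.5, general baseline rule: "the last valid, non-missing value prior to the Reference start date will be considered as baseline value".
- Section 4.5, repeated measurements at the same visit: after randomization, the first observation is summarised unless the investigator gave a special reason for the extra one.
- Section 6.1.2: for the baseline table, "the measurement closest to the administration of study drug will be used as baseline". That table includes "volume of largest fibroid, volume of 3 largest fibroids, location of largest fibroid (measured by ultrasound) at baseline", and also baseline uterine volume.

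**The concern.** A rule that takes the last value already settles which of several baseline scans to use. The smallest-value rule is therefore not filling a gap; it gives a second answer to the same question. One rule is specific to the variable and the other is specific to multiple scans, so neither is plainly the exception to the other. Two programmers who both follow the section could report different percent changes and different counts of subjects with at least a 25% reduction.

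Three further points are left unreconciled:

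- The two rules draw the baseline window differently.
- The denominator need not match the baseline volume tabulated in the same report.
- Taking the largest post-baseline volume in an interval does not sit with taking the first observation at a visit.

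The section also does not tell the reader that the smallest/largest pairing is a worst-case display.

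**Working it through.** The SAP states no numerical result on this point, so there is no figure to reproduce. The check is algebra plus a side-by-side reading.

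**1. When the two baseline rules differ.** Percent change = 100 × (post − baseline) / baseline. With one baseline scan the rules agree. With two or more they differ whenever the last scan is not the smallest. If a subject's k baseline scans are exchangeable (an assumption), the last is not the smallest with probability 1 − 1/k, which is 50% for k = 2 and 67% for k = 3.

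**2. Effect on one subject.** Take baselines of 90 mL then 100 mL, and one post-baseline volume of 75 mL (illustrative values).

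| Baseline rule | Denominator | Percent change | At least 25% reduction? |
|---|---|---|---|
| Last before randomization | 100 mL | 75/100 − 1 = −25.0% | Yes |
| Smallest in the period | 90 mL | 75/90 − 1 = −16.7% | No |

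Measured from the last baseline, the fall needed to count as a responder under the smallest-value rule is 1 − 0.75 × (smallest/last). This is 32.5% if the smallest is 10% below the last, and 40% if it is 20% below.

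**3. Windows.** The baseline phase ends the day before the reference start date.

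| Scan | Before randomization? | In the baseline phase? |
|---|---|---|
| Vilaprisan, after randomization and before the day of first intake | No | Yes |
| Group B, on the day of randomization but before it | Yes | No |

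The mismatch can therefore arise in either arm, in opposite directions. Whether such scans occur depends on a visit schedule that the SAP does not show.

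**4. Direction of the smallest/largest pairing.** Percent change rises with the post-baseline value and falls with the baseline value. Largest post over smallest baseline is therefore at or above the change from any other pairing of the same scans, so it never shows more shrinkage than another choice.

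**5. Size, under stated assumptions only.** To isolate the baseline conflict, give a subject two baseline scans and one post-baseline scan. Assume a true reduction of 35% and lognormal scan errors with a common correlation. None of these inputs is in the SAP. The probability of counting as a responder then changes as follows.

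| Scan CV | Error correlation | Last baseline | Smallest baseline |
|---|---|---|---|
| 10% | 0.8 | 98.9% | 97.8% |
| 20% | 0 | 69.5% | 55.1% |
| 20% | 0.5 | 76.5% | 64.1% |
| 20% | 0.8 | 87.3% | 79.2% |
| 30% | 0 | 63.5% | 47.9% |

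The drop runs from 1.1 to 15.6 percentage points, and applies only to subjects with a repeat baseline scan. If a fraction f of subjects have one, the drop in the reported rate is f times this. At f = 10% it is about 0.1 to 1.6 points. The SAP does not give f.

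**The case against.** The strongest reply is that smallest baseline with largest post-baseline is a deterministic, pre-specified convention that works against showing efficacy. Worst-value selection runs through this SAP: the UFS-QoL scores, BMD beyond month 14, endometrial histology, laboratory values, estradiol and liver parameters. That stands. A reader might infer that the pairing is itself an error and must be demoted to a sensitivity table, but the SAP does not support that; it is a choice open to debate. What the reply does not remove is the contradicting definition in the first bullet. Those other sections also describe their selection as worst or worst-case, and this one does not.

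A second reply is that the baseline-table mismatch is not a contradiction. The general baseline rule in Section 4.5 is only a default, and for the three-fibroid and uterine volumes the smallest-value rule can be read as a specific exception to it. That also stands, and a footnote is enough there.

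A third is that Section 6.2.3.3 calls for analysis by visit as well as by Intervals B, while the largest-value rule is limited to Intervals B. A by-visit display using the first observation may therefore be intended. That is possible, but the section does not say so.

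Finally, these are descriptive other-efficacy variables in a study that was stopped early. That limits the weight of the point without resolving the conflict.

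**Conclusion.** The point holds for the largest-fibroid baseline. Section 6.2.3.3 gives two rules for the same case, they can change a subject's responder status, and nothing says which applies. The window mismatch, the unlabelled worst-case pairing, the possible difference from the baseline table and the unreconciled first-observation rule belong to the same correction.

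The effect is exactly zero for subjects with one baseline scan. The trial-level effect is unknown and could be near zero, because the frequency of repeat scans and the measurement error are not given.

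Three stronger readings are not supported:

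- **That reported shrinkage always lies below true shrinkage.** The direction holds only against other choices from the same scans; random scan error can still push an individual result either way.
- **That responder rates would fall by a large known amount.** The larger falls obtainable by simulation apply the largest-post rule as well, which Section 6.2.3.3 does not contradict, and assume that every subject has repeats.
- **That the comparison between arms is distorted.** Opportunities for repeat scans may differ, since vilaprisan intervals include the break and group B intervals are 84 days. The SAP gives no basis for a size or direction.

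The primary BMD variable and the secondary bleeding-days variable are not affected.

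**What to change.** 1. State one baseline rule with one anchor date for all six ultrasound variables. The last valid value before the reference start date is preferable, because it agrees with the general rule in Section 4.5 and with Section 6.1.2. Delete the conflicting text in Section 6.2.3.3.
2. Say whether the first-observation rule in Section 4.5 or the largest-value rule governs post-baseline repeats, and whether by-visit and by-interval displays differ in this.
3. If smallest/largest is kept, remove the last-before-randomization definition from the first bullet. Label the table worst-case and footnote that its baseline may differ from the baseline table. Optionally add a display using the last baseline and a post-baseline scan chosen without regard to its value.

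The cost is SAP wording and a change in record selection; no new data are needed. If the last-value rule is adopted, the main display is no longer worst-case at baseline.

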6.2.3.4 Percentage of subjects undergoing surgical treatment

The number and percentage of subjects undergoing surgical treatment will be evaluated in a frequency table by treatment group and by TP and FUP (time interval B). In contrast to other efficacy variables, any fibroid surgeries performed during FUP of subjects who did not start the planned last TP, will be evaluated for FUP rather than for break period.

6.2.3.5 Patient/Clinician-reported outcomes

6.2.3.5.1 Change in UF-DSD individual items compared to baseline

The UF-DSD will be completed daily using the eDiary. The UF-DSD includes 2 items to assess swelling and bloating symptoms using a 5-graded Likert-type severity rating ('no symptom' to 'very severe symptom'), and 2 items using a 0 to 10 numerical rating scale to assess pain at its worst in the abdominal/pelvic and lower back areas with 0 indicating "no pain" and 10 "pain as bad as you can imagine."

Bulk symptoms and pain represent potential domains. Additionally, intake of pain medication is investigated using a 4-point verbal rating scale (no; yes, over the counter (non-prescription) pain medication; yes, prescription pain medication; or yes, both over the counter and prescription pain medication).

Following variables for each domain will be summarized by treatment group and time interval D. For the vilaprisan treatment groups, this will be presented by TP, break, and FUP within treatment group. For the treatment group B, this will be presented by TP and FUP. Line plots with standard deviation (SD) will be generated.

Bulk symptoms (items 1 and 2)

- Mean of subjects' relative frequencies of the scores during baseline (last 28 days before first dose of study drug) and each 28-day period after start of treatment, as well as change from baseline
- Mean of subjects' worst 7 scores during baseline (last 28 days before first dose of study drug) and each 28-day period after start of treatment, as well as change from baseline

Pain (items 3 and 4)

- Mean numerical rating score and absolute change from baseline (last 28 days before first dose of study drug) to each 28-day period after start of treatment
- Mean numerical rating score of the 7 days with worst pain and absolute change from baseline (last 28 days before first dose of study drug) to each 28-day period after start of treatment

For medication intake (item 5), means of proportion of days with "Yes, over the counter (non-prescription) pain medication", "Yes, prescription pain medication" or "Yes, both (over the counter and prescription pain medication)" during baseline (last 28 days before first dose of study drug) and each 28-day period after start of treatment will be summarized, as well as change from baseline.

6.2.3.5.2 Change in Uterine Fibroid Symptom and Quality of Life questionnaire (UFS-QoL) scores compared to baseline

The UFS-QoL consists of 37 items including an 8-item symptom severity scale and 29 health-related quality of life questions, which comprise 6 subscales: concern, activities, energy/mood, control, self-consciousness, and sexual function. Details regarding the calculation of scales are provided in Appendix 1. For each subscale (including symptom severity scale, Revised Activities and Revised HRQoL total score), raw scores and transformed scores will be summarized by treatment group and time interval D, as well as change from baseline. The worst measurement within the time interval will be used for calculations. Largest value for Symptom Severity scale and lowest value for HRQoL scale. Line plots with SD will be generated.

